			3.6.1.2 Clinical Laboratory Tests	
			3.6.1.3 Vital sign	
			3.6.1.4 ECG 3.6.1.5 Physical Examination	
		3.6.2	The Effect of Tralokinumab on Pulmonary Function	
		3.6.3	The Effect of Tralokinumab on Patient Reported Outcomes	
		3.6.4	The Pharmacokinetics (PK) and Immunogenicity of Tralokinumab	
	3.7		naries to Support the Exploratory Objectives	
4			Data	
•				

5	General Statistical Conventions	39
6	References	40

Version 2.0

List of Abbreviations:

Abbreviation or Specialized Term	Definition
ACQ-6	Asthma Control Questionnaire (6-item version)
ADA	anti-drug antibodies
AE	adverse event
AHR	airway hyperresponsiveness
AQLQ(S)	Asthma Quality of Life Questionnaire (Standardized Version)
ASMA	Assessing Symptoms of Moderate-to-severe Asthma
ATS	American Thoracic Society
BAL	bronchoalveolar lavage
βHCG	β human chorionic gonadotrophin
BMI	body mass index
CI	confidence interval
COPD	chronic obstructive pulmonary disease
CRF	case report form
CT	computed tomography
DPI	dry powder inhaler
DNA	deoxyribonucleic acid
ECG	electrocardiogram
ePRO	electronic Patient-reported Outcome
ERS	European Respiratory Society
EU	European Union
FEIA	Fluorescent Enzyme Immunoassay
FEV_1	forced expiratory volume in 1 second
FEV ₆	forced expiratory volume in 6 second
FSH	follicle-stimulating hormone
FVC	forced vital capacity
HIPAA	Health Insurance Portability and Accountability Act
GCP	Good Clinical Practice
GINA	Global Initiative for Asthma
HIV	human immunodeficiency virus
HRCT	high-resolution computed tomography
HRQoL	health-related quality of life

Protocol CD-RI-CAT-354-1049/ D2210L00001

Version 2.0

HRU	Healthcare Resource Utilization
IC	inspiratory capacity
ICF	informed consent form
ICH	International Conference on Harmonisation
ICS	inhaled corticosteroid(s)
IEC	Independent Ethics Committee
IgG	immunoglobulin G
IgG4	immunoglobulin G4
IgE	immunoglobulin E
IL-13	interleukin-13
IRB	Institutional Review Board
ITT	Intent-to-Treat
IV	intravenous
IXRS	interactive voice/web response system
LABA	long-acting β2 agonist
MAb	monoclonal antibody
MDI	metered dose inhaler
mRNA	messenger ribonucleic acid
OCS	oral corticosteroids
PEF	peak expiratory flow
PFM	peak flow meter
РК	pharmacokinetics
PK/PD	pharmacokinetic/pharmacodynamic
РР	per protocol
Q2W	every 2 weeks
Q4W	every 4 weeks
SABA	short-acting β2 agonist
SAE	serious adverse event
SC	subcutaneous
SID	subject identification
SMC	Safety Monitoring Committee
SUSARs	suspected unexpected serious adverse reactions
TB	tuberculosis
Th2	T helper 2
WPAI-Asthma	Work Productivity and Activity Impairment Questionnaire - Asthma

Version 2.0

1 Introduction

This document describes the statistical methodology for CD-RI-CAT-354-1049/ D2210L00001, a Phase 2b, Randomized, Double-blind Study to Evaluate the Efficacy of Tralokinumab in Adults with Uncontrolled, Severe Asthma. Some background information and an overview of the study design are provided in Section 2. Section 3 and onwards of the document details the statistical summaries relating to each study objective as well as describing general conventions and definitions. A separate statistical programming plan (SPP), containing table templates and specifications, has also been created to be used in conjunction with this document.

2 Background

Asthma is a chronic inflammatory disease in the airways characterized by bronchial hyperactivity and reversible limitation of airflow that causes wheezing, shortness of breath, cough, and chest tightness.

Approximately 5% to 10% of asthma patients have severe asthma, which may be inadequately controlled by ICS and LABA combinations together with additional controller therapies (Brightling et al, 2008). These patients are at risk of asthma exacerbations (Tough et al, 1998; Turner et al, 1998) and have the greatest medical need among the asthmatic population today and represent the greatest economic cost (> 50% of total asthma-related health care costs; Antonicelli et al, 2004; Serra-Batlles et al, 1998; Barnes et al, 1996). Thus, there is a clear medical need for patients with severe asthma who are unable to gain complete asthma control using currently available therapies.

Interleukin-13 (IL-13) is a member of the interleukin family of cytokines and is secreted predominantly by CD4+ T-helper-2 (Th2) cells. Interleukin-13 receptors are expressed on a number of cell types including key cells involved in asthma (Hershey, 2003). There is considerable evidence that IL-13 is a key mediator in the pathogenesis of established asthmatic disease and may have a number of effects (Hershey, 2003; Saha et al, 2008)

Tralokinumab is a human recombinant monoclonal antibody (MAb) of the immunoglobulin G4 (IgG4) subclass that specifically binds human IL-13, blocking interactions with the IL-13 receptor.

2.1 Study Overview

This is a Phase 2b, randomized, double-blind, placebo-controlled, parallel-arm, multicenter study to evaluate the efficacy and safety of two SC treatment regimens of tralokinumab in adult subjects with uncontrolled, severe asthma requiring high-dose ICS and LABA with or without additional controller medications (high-dose ICS defined as a total daily dose $> 500 \mu g$ fluticasone DPI or $> 440 \mu g$ MDI; GINA, 2009; National Heart, Lung, and Blood Institute, 2007). Approximately 100 sites around the world will participate in the study. A total of approximately 390 subjects will be randomized in a 1:1 ratio to one of 2 cohorts (Cohort 1 or Cohort 2). Within each cohort, subjects will be randomized in a 2:1 ratio to receive tralokinumab (300 mg) or placebo as follows:

Cohort 1: Tralokinumab 300 mg (n = 130) or Placebo (n = 65) as 2 SC injections Q2W for 50 weeks for a total of 26 doses

Cohort 2: Tralokinumab 300 mg (n = 130) or Placebo (n = 65) as 2 SC injections Q2W for 12 weeks followed by Q4W for 38 weeks for a total of 16 doses

Subjects will be stratified at screening by the number of asthma exacerbations in the past 12 months (2 versus > 2 but \leq 6 exacerbations) and by chronic OCS use (presence versus absence). To maximize the probability of obtaining treatment balance within Japanese population for the purpose of PMDA filing, the Japanese will be randomized separately.

A 5-week screening/run-in period (Week -5 to -1 [Day -1) will precede investigational product administration. Starting at Week -4 (Day -28), subjects will receive a fixed-dose combination product of fluticasone/salmeterol, either as an MDI (230 μ g/21 μ g) at a dose of 2 inhalations twice per day or as a DPI (500 μ g/50 μ g) at a dose of one inhalation twice per day. Sites/subjects will be permitted to use either presentation of fluticasone/salmeterol if approved and available for use in their country. If the subject is also taking additional asthma controller medications (including leukotriene modifiers, theophylline, chromones, or OCS \leq 20 mg/day), then these medications should be continued at a stable dose during the screening/run-in period. During the study, subjects may use inhaled reliever therapy (e.g., SABA or short-acting anticholinergic) on an as-required basis as documented in their Personalized Asthma Action Plan.

Subjects will continue to receive the same fixed-dose combination product of fluticasone/salmeterol with or without additional asthma controller medications at a stable dose during the treatment period and through Week 53. Subjects who experience an asthma

Version 2.0

exacerbation during the treatment period will be treated accordingly and will remain in the study.

Subjects will return to the clinic at Week 53 for an assessment of the efficacy endpoints. Subjects will have 3 additional follow-up visits at Weeks 59, 67, and 75. After the Week 53 visit, background medications may be changed as deemed necessary by the investigator.

As part of the study, selected sites will take part in a substudy using HRCT scanning to measure potential airway wall structural changes including airway wall thickness. Sites will be selected on their ability and willingness to carry out the scans. Participation in this substudy is optional for subjects at the selected sites. An adequate number of sites will be identified in order to target recruitment of approximately 40 subjects into each of the 2 treatment groups for the HRCT substudy.

[figure not shown]

Figure 2.1-1 Study Flow Diagram

Q2W = every 2 weeks; Q4W = every 4 weeks; Wks = Weeks

2.2 Randomization and Blinding

2.2.1 Subject Randomization Procedures and Treatment Allocation

An IXRS will be used for randomization to a cohort and assignment of blinded investigational product kit numbers. A subject is considered randomized into the study when the investigator or designee notifies the IXRS that the subject meets eligibility criteria and the IXRS provides the assignment of blinded investigational product kit numbers to the subject.

Subjects will be randomized in a 1:1 ratio to one of 2 cohorts. Within each cohort, subjects will be randomized in a ratio of 2:1 to receive SC tralokinumab (300 mg) or placebo. Subjects will be stratified at screening by the number of asthma exacerbations in the past year (2 versus > 2 but \leq 6 exacerbations) and by chronic OCS use (presence versus absence). To maximize the probability of obtaining treatment balance within Japanese population for the purpose of PMDA filing, the Japanese will be randomized separately.

2.2.2 Blinding

This is a double-blind study in which tralokinumab and placebo are visually distinct from one another. Neither the subject nor any of the investigator or sponsor staff who are involved in the treatment or clinical evaluation of the subjects will be aware of the treatment received (International Conference on Harmonisation [ICH] E9). Since tralokinumab and placebo are visually distinct, investigational product will be handled by an unblinded investigational product manager at the site and will be administered by an unblinded study team member who will not be involved in the management of study subjects. (These could be the same person.) An independent investigational product monitor will also be unblinded to perform investigational product accountability. In the event that the treatment allocation for a subject becomes known to the investigator or other study staff involved in the management of study subjects, or needs to be known to treat an individual subject for an AE, the sponsor must be notified immediately by the investigator and if possible, before unblinding.

Two formal analyses (Stage 1 analysis and Stage 2 analysis) as well as an interim analysis will be performed for the study. The Stage 1 analysis will be conducted after the last subject has completed the Week 53 visit. The Stage 2 analysis for long-term safety follow-up will be performed after all subjects have completed the study. Study site personnel and the subjects will remain blinded to the treatment assignment for individual subjects until the end of the follow-up period to Week 75. MedImmune will be unblinded at the Stage 1 primary analysis.

Version 2.0

The interim analysis will be performed by a limited number of sponsor personnel who are not involved in the conduct of the study.

2.3 Sample Size Considerations

Sample size calculations have been performed by simulations combined with normal approximation. Simulations assume the data follow exact Poisson distribution. Simulated data have been analyzed using Poisson regression without adjusting for overdispersion.

A total of 390 subjects will be randomized in a 1:1 ratio to one of 2 cohorts (Cohorts 1 or Cohort 2). Within each cohort, subjects will be randomized in a 2:1 ratio to receive SC tralokinumab (300 mg) or placebo. The primary analysis will be based on the ITT population.

Fifty-three subjects per treatment arm would be required to detect a 40% reduction in annual asthma exacerbation rate for each tralokinumab cohort compared to placebo assuming an annual exacerbation rate in placebo group of 1.2 with 80% power and a significance level of 0.1. Sample size was increased to 65 per treatment arm to accommodate overdispersion of 1.2. Recent data suggest that approximately half of asthmatic subjects may have a molecularly distinct subtype of asthma characterized by IL-13-driven inflammation; it is reasonable to hypothesize that these IL-13-positive subjects will have the optimal response to tralokinumab therapy. Therefore the sample size has been increased from 65 to 130 subjects per treatment arm to allow for a subanalysis to explore the relationship between the clinical response to tralokinumab and the presence of peripheral blood biomarkers associated with upregulation of IL-13 in the asthmatic lung. In the event that the clinical response is observed only in IL-13-positive subjects, this sample size retains adequate power to detect a difference in the asthma exacerbation rate comparing IL-13-positive tralokinumab treated subjects versus placebo. As presented below, the power to detect a 40% reduction in the exacerbation rate will depend upon the positive predictive value of the peripheral blood biomarker with respect to actual lung IL-13 expression (Table 1).

Table 1	Peripheral Blood Biomarker Positive Predictive Value
Table I	relipheral blood blomarker Positive Predictive value

Peripheral Blood Biomarker PPV	Two-sided alpha	Power (Individual Tralokinumab vs. Placebo)
100%	0.1	81.9%
90%	0.1	73.5%
80%	0.1	61.6%
75%	0.1	57.3%

IL-13 = interleukin-13; PPV = positive predictive value

The accrual of asthma exacerbations is monitored during the study and blinded estimates of the annual asthma exacerbation rate in the placebo group are calculated. These estimates are consistently lower than the planned placebo rate of 1.2 exacerbations per year. In order to maintain adequate power to detect a 40% reduction in the annual asthma exacerbation rate for each tralokinumab cohort compared to placebo, the significance level for the data analysis will be raised from two-sided 0.1 to two-sided 0.15.

Sites in Japan will randomize approximately 65 Japanese subjects as part of the overall sample size. In the event that enrollment of the Japanese subjects is significantly delayed, and to ensure a timely Stage 1 analysis, non-Japanese sites may contribute sufficient subjects to reach the sample size required for the Stage 1 analysis (at least 390 subjects). In this event, sites in Japan will be permitted to continue enrollment until such time as approximately 65 Japanese subjects have been enrolled.

3 Statistical Methods

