3.1 General Considerations

Two formal analyses (Stage 1 analysis and Stage 2 analysis) as well as an interim analysis are planned for the study.

The Stage 1 analysis for the overall population will be conducted after the last non-Japanese subject has completed the Week 53 visit or discontinued prematurely (this analysis will include all Japanese subjects who have completed Week 53). The Stage 2 analysis for long-term safety follow-up will be performed after all subjects have completed the study or discontinued prematurely. During the Stage 1 analysis, all the efficacy and safety data

Version 2.0

collected will be analyzed. Pairwise comparisons between individual tralokinumab treatment groups and combined placebo will be conducted. The primary analysis for which the study is powered will be completed in the Stage 1 analysis, and the analyses based on primary efficacy endpoint will be repeated for overall population (which includes all subjects enrolled into the study) at the end of the study as sensitivity analysis.

The interim analysis will be conducted after the last non-Japanese subject randomized into the study has completed the Week 39 visit or discontinued prematurely. All data available will be analyzed as part of the interim analysis. The details of the interim analysis will be specified in unblinding plan for interim analysis.

The overall type I error rate (two-sided) will be controlled at the 0.15 level using O'Brien-Fleming alpha spending function based on the actual person-years follow-up observed. For example, if the information fraction at the interim analysis is 88%, then the two-sided type I error rate will be 0.105 for the interim analysis and 0.128 for final analysis, respectively. The interim analysis will have minimal impact on the power of the study at the final analysis, which is estimated to be approximately 78%.

Three sets of analyses will be performed at Stage 1. They are: 1) analyses based on overall population; 2) analyses for Japan only subjects (n=45); and 3) analyses for non-Japanese subjects. The go/no-go decision will be based on stage 1 analysis for overall population.

In addition, for PMDA consultation, the same analyses for all Japan subjects (n=64) will be conducted when all Japan subjects complete week 53 follow-up or discontinue prematurely.

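### Table 1 and the claim of adequate power in IL-13-positive subjects were not updated when alpha was raised and the placebo rate ran low, and the 78% study power has no stated inputs

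*SAP*

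**What the plan says.** All of this is current text in the SAP.

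- **Section 2.3, design basis.** "Fifty-three subjects per treatment arm would be required to detect a 40% reduction in annual asthma exacerbation rate", "assuming an annual exacerbation rate in placebo group of 1.2 with 80% power and a significance level of 0.1". Then: "Sample size was increased to 65 per treatment arm to accommodate overdispersion of 1.2".
- **Section 2.3, doubling.** About half of asthmatic subjects are taken to be IL-13-positive, so "the sample size has been increased from 65 to 130 subjects per treatment arm to allow for a subanalysis". The conclusion is that "this sample size retains adequate power to detect a difference in the asthma exacerbation rate comparing IL-13-positive tralokinumab treated subjects versus placebo". Table 1 follows, with a printed two-sided alpha of 0.1 and powers of 81.9, 73.5, 61.6 and 57.3% at PPV 100, 90, 80 and 75%. The text says that power depends on the PPV.
- **Section 2.3, later paragraph.** On the blinded monitoring: "These estimates are consistently lower than the planned placebo rate of 1.2 exacerbations per year". To keep power for each tralokinumab cohort against placebo, "the significance level for the data analysis will be raised from two-sided 0.1 to two-sided 0.15". No replacement placebo rate is given.
- **Section 3.1.** With 88% information at the interim, the nominal levels are 0.105 and 0.128. On power, the plan says "The interim analysis will have minimal impact on the power of the study at the final analysis, which is estimated to be approximately 78" per cent. It gives no rate, overdispersion, sample size or comparison for that figure. The same section assigns control of the family-wise error for the primary endpoint to the Hochberg procedure, in a paragraph that begins with biomarker subgroups, and does not list the hypotheses in the family.

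**The concern.** The adequacy sentence and Table 1 sit a paragraph above text that replaces one of their inputs (alpha) and reports that another (the placebo rate) is not being seen. The two changes pull in opposite directions: a higher alpha raises power and a lower rate reduces it. The reader therefore cannot tell whether Table 1 is now too high or too low.

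The 78% is the only later clue, and it is far below what the Table 1 inputs imply for the full-size comparison. The marker analysis is the stated reason for doubling enrolment. If its real power is near one half, a null result read against 81.9% would be taken as evidence of no effect when the trial had little chance of showing one.

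**Working it through.** **Inputs.** From section 2.3: placebo rate λ = 1.2 per year, true rate ratio 0.60, overdispersion φ = 1.2, alpha 0.10, 65 then 130 per arm. Half of 130 gives 65 marker-positive subjects per arm. From section 3.1: final-stage alpha 0.128 (its 88% example). Assumptions: one year of follow-up each; false-positive subjects have no treatment effect; the combined placebo group equals one active arm (65 + 65 = 130).

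**Formula.** Wald test on the log rate ratio:

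SE = √[φ(1/(nλ) + 1/(nλ·RR))], power = Φ(|ln RR|/SE − z), RR = 0.6·PPV + (1 − PPV).

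z is 1.645 at alpha 0.10, 1.522 at 0.128 and 1.440 at 0.15.

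**Step 1: the plan's sample sizes.** n = (1.645 + 0.842)² × (1/1.2 + 1/0.72)/(ln 0.6)² = 52.65, so 53, as stated. Multiplying by 1.2 gives 63.2, so 64, against 65 stated.

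**Step 2: Table 1** (λ = 1.2, φ = 1.2, n = 65, alpha 0.10). At PPV 100%: SE = 0.2025, 0.5108/0.2025 = 2.522, and Φ(2.522 − 1.645) = 81.0%.

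| PPV | RR | Recomputed | Table 1 |
|---|---|---|---|
| 100% | 0.60 | 81.0% | 81.9% |
| 90% | 0.64 | 72.7% | 73.5% |
| 80% | 0.68 | 63.1% | 61.6% |
| 75% | 0.70 | 57.9% | 57.3% |

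All four agree within 2 points. Power depends only on λ/φ, so the table fixes a ratio of about 1.0, not the two values separately.

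**Step 3: the ITT comparison at the same inputs.** With n = 130, SE = 0.1432 and 0.5108/0.1432 = 3.567. Power is 97.3% at alpha 0.10 and 98.0% at 0.128. It is not 78%.

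**Step 4: reading A, the 78% is the ITT comparison at 0.128.** The standardised effect must be 0.772 + 1.522 = 2.294. The marker-positive comparison has half the subjects, so at PPV 100% it is 2.294/√2 = 1.622, and power is Φ(1.622 − 1.522) = 54%. For PPV 100, 90, 80 and 75% the powers are 54, 47, 40 and 37% (57, 50, 43 and 40% at alpha 0.15). These hold for any pair of λ and φ that gives 78%. With φ = 1.2 the implied rate is about 0.50; with φ = 1.0 it is about 0.41. If the 78% instead means rejection at either the interim or the final analysis, PPV-100% power is about 52%.

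**Step 5: reading B, the 78% is a 65-per-arm comparison at 0.128.** With φ = 1.2 the implied rate is about 0.99. Marker-positive power is then 78, 70, 61 and 56%, close to Table 1. At that rate, however, the 130-per-arm comparison has 0.5108/SE = 3.245, and Φ(3.245 − 1.645) = 94.5% power at alpha 0.10, before any increase in alpha.

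**Step 6: range over the unstated rate** (φ = 1.2, n = 65, alpha 0.128, PPV 100/90/80/75%).

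| Placebo rate | Marker-positive power |
|---|---|
| 1.2 | 84/77/68/63% |
| 0.9 | 75/66/58/53% |
| 0.7 | 66/58/50/46% |
| 0.5 | 54/47/40/37% |

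**Step 7: Hochberg.** A comparison with 80% power at 0.15 has Φ(1.440 + 0.842 − 1.522) = 77.6% at 0.128, which matches the stated 78% with no multiplicity adjustment. If the Hochberg family holds the two regimens, simulation with a shared placebo arm gives per-regimen power of about 75% if both regimens work and about 68 to 69% if only one does.

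**The case against.** A reader might infer that Table 1 and the 78% flatly contradict each other and that no placebo rate reconciles them. The documents do not support that. The 78% has no stated inputs, section 2.3 builds its 80% on 65 per arm, and a rate of about 0.99 on that basis gives both 78% and nearly the printed table. A rate of 0.99 is also below 1.2, as the monitoring reports. This stands, so the conflict is conditional on how the 78% is read.

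Reading B does not clear the text, however. Section 3.1 speaks of the power of the study, close to its mention of the primary analysis for which the study is powered, and section 2.3 makes that the ITT analysis. Under reading B the cohort comparisons already had about 94.5% power at alpha 0.10, so the reason given for raising alpha would not apply.

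Two further points stand. The rate of 1.2 was never formally replaced, and the alpha change alone would raise PPV-100% power from 81 to 86% at rate 1.2, so the direction of the error depends on an unstated number. The marker analysis is also exploratory: section 3.7 reports it separately, section 3.1 assigns it to an exploratory analysis plan, and the go/no-go decision uses the overall population.

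A reader might also infer that the 78% ignores Hochberg. That is not established, because section 3.1 does not list the family. The match to an unadjusted test is suggestive only.

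**Conclusion.** Table 1 and the adequacy sentence rest on an alpha that the plan has replaced and on a placebo rate that it says is not being observed, and they were left unchanged. The 78% cannot come from 130 per arm at the Table 1 inputs, where power is 97 to 98%. On the natural reading, marker-positive power is about 54, 47, 40 and 37% instead of about 82, 73.5, 62 and 57%. On the other reading Table 1 nearly holds, but the justification for raising alpha fails. Either way something in sections 2.3 and 3.1 needs correcting. Even as printed, power of 57 to 62% at PPV 75 to 80% sits poorly with the word adequate.

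These figures assume a 40% reduction in true positives, none in false positives, half of subjects marker-positive, one year of follow-up and a final alpha of 0.128. The Hochberg loss, about 3 points if both regimens work and about 10 if one does, applies only if the family includes the two regimens.

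This should be fixed. It is not critical, because it changes no model, boundary or decision rule.

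**What to change.** - In section 3.1, state the current blinded placebo-rate estimate, the overdispersion, the sample size per arm and the comparison behind the 78%.
- In section 2.3, recompute Table 1 at that rate and overdispersion and at the current final-stage alpha. Recompute the 78% on the same basis.
- Replace the adequacy sentence with the recomputed figures, across the PPV range.
- State which hypotheses are in the Hochberg family and whether the 78% allows for it. If it does not, give the power under the procedure.

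The cost is SAP wording and a short calculation, with no extra patients. The stated powers may become less favourable.
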